## 202 Inverse probability of censoring weighing

- In this study, we will estimate the inverse probability of censoring weights by fitting a pooled logistic
   model for the monthly probability of remaining uncensored, including variables for time (in its linear
- and/or quadratic terms depending on the data structure) and the baseline covariates. To avoid
  undue influence of outliers, weights will be truncated at the 99.5th percentile in case of extreme
  weights.
- 208 The inverse probability of censoring weighting will be built using two different models including a
- 209 different set of covariates as shown in the following table.

Variables	Model 1	Model
Age	Y	Y
Sex (male vs female)	Y	Y
Body Mass Index	N	Y
Socioeconomic deprivation	Y	Y
Smoking status	N	Y
Alcohol intake	N	Y
Gout duration (years)	Y	Y
Subcutaneous tophi (y/n)	Y	Y
Number of anti-inflammatory prescriptions (colchicine, NSAIDs, and corticosteroids) in	Y	Y
12 months before ULT initiation		
Number of consultations in primary care for gout and number of hospitalisations for	Y	Y
gout in the 12 months before ULT initiation		
ULT molecule (i.e., febuxostat, allopurinol, uricosurics)	Y	Y
ULT dose (high vs low starting dose)	Y	Y
Co-prescription of gout flare prophylaxis with colchicine and/or non-steroidal anti-	Y	Y
inflammatory drugs on the date of ULT initiation (i.e., prescription length ≥21 days)		
Charlson comorbidity index	N	Y
Cardiovascular comorbidities not included in the Charlson Comorbidity index (i.e.,	Y	Y
hypertension, atrial fibrillation, and hypercholesterolemia)		
Acute or chronic ischaemic heart disease, heart failure, diabetes with and without	Y	Y
target organ damage, chronic kidney disease (stage 3,4,5), dementia, peripheral		
vascular disease, COPD, cancer, HIV/AIDS		
History of cardiovascular events before ULT initiation	Y	Y
European Society of Cardiology cardiovascular risk	Y	Y
Number of consultations in primary care for any reason and number of hospitalisations	Y	Y
for any cause in the 12 months before ULT initiation		
Proportion of days covered by ULT between the date of ULT initiation and the end of	Y	Y
the grace period		N N
Low-dose ASA	Y	Y
Non-ASA antiplatelet agents	Y	Y
Statins	Y	Y
Fibrates	Y	Y
Other lipid-lowering agents	Y Y	Y
Potassium-sparing diuretics	Y Y	Y
Thiazides		Y
Loop diuretics	Y	Y
Beta-blockers	Y Y	Y
Calcium-channel blockers	Y Y	Y
Angiotensin-converting enzyme inhibitors	Y Y	Y
Angiotensin receptor blockers		Y
Other anti-hypertensive agents	Y	Y
Nitrates	Y	Y
Ves, N: no.	Y	Y

211

212 Model 1 will be used to meta-analyse the results from CPRD and VEGA datasets. Model 2 will be

213 used to test the internal validity of the association between exposure and outcome and to check

whether the variables available only in CPRD could represent major confounders.

215 Missing data

216 BMI, smoking status, alcohol intake status, and socioeconomic deprivation can have missing data in

217 CPRD. The pattern of missingness will be compared and missingness at random assumed. Missing

- 218 data will be imputed using chained equations. BMI, smoking status, alcohol intake status, and
- 219 socioeconomic deprivation will be modelled using multinomial logistic regression.
- 220 Subgroup analyses
- 221 We will perform some sensitivity analyses to test the robustness of the association between the 222 exposure and the outcome.
- We will consider a SU target of ≤300 micromol/l to define the T2T-ULT arm and we will compare
   it with not achieving a SU target of ≤360 micromol/l,
- 225 We will further censor the follow-up when people will discontinue ULT,
- We will exclude from the FAF-ULT arm, those patients who will not have measured serum urate
   levels within 12 months after ULT initiation.
- 228 Also, we will stratify the analyses using the following prognostic factors:
- 229 Age (>65 and ≤65 years),
- 230 Gender (male and female).
- 231 Feasibility count and sample size considerations
- 232 In a previous study, we identified 96,000 patients with incident gout in CPRD. Of them, 48%

233 (~46,000) were ever prescribed ULT, and 28% (~12,000) and 16% (~7,000) achieved serum urate

- targets of  $\leq$ 360 micromol/l and  $\leq$ 300 micromol/l within 1 year after the first ULT prescription, respectively [2].
- 236 Approximately, 20,000 patients with an incident diagnosis of gout were ascertained in VEGA. Of
- them, 42% (~8,000) were prescribed ULT [30]. We assume a similar rate of success as in CPRD. Thus,
- data for approximately 14,000 exposed and 30,000 unexposed patients and 8,000 exposed and
- 239 30,000 unexposed patients will be available for the main aim and the secondary aim, respectively.
- Based on these data, our study will have more than 99% power to detect a risk difference of 1/1,000
- person-years assuming a rate of MACE of 17/1,000 person-years [5] in the unexposed and an alphaerror of 0.025.
- 243 Ethics, funding, and patient partner in research involvement
- 244 This study was approved by Clinical Practice Research Datalink's Research Data Governance
- 245 (protocol 23\_002701), which has overarching research ethics committee approval for research
- studies using anonymous data (reference 05/MRE04/87). Practices that contribute data to the
- Clinical Practice Research Datalink allow the use of anonymized patient data for approved researchprojects and additional patient consent is not required.
- 249 This study followed the recommendations of the RECORD (Reporting of Studies Conducted using
- 250 Observational Routinely Collected Data) statement.
- 251 Patient organisations (The UK Gout Society) were involved in prioritising the research question.
- 252 This project was supported by a research grant from the Foundation for Research in Rheumatology
- 253 (FOREUM). The funder had no role in study design, data collection, data analysis, data interpretation
- 254 or writing of the report.

255

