### 148 Follow up

- 149 People will be followed up from the first ULT prescription to the earliest date of a cardiovascular
- event, transfer out of the primary-care practice, death, 5 years from the first ULT prescription, studyend, and last consultation in primary care.
- Artificial censoring will be applied as follows: 1) clones assigned to the T2T-ULT arm will be censored at 12 months from ULT initiation if they do not achieve the serum urate target, 2) clones assigned to the FAF-ULT arm will be censored at the time they achieve the serum urate target within 12
- 154 to the FAF-OLT and will be censored at the time they achieve the seruin drate target v
- 155 months after the first ULT prescription.
- 156

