## 157 Covariates

- We will collect the following covariates ascertained on or before ULT initiation to build the inverseprobability of censoring weighting as detailed above:
- demographics: age, sex (male or female), latest body mass index (BMI) available only in CPRD,
   socioeconomic deprivation assessed using the index of multiple deprivation (IMD) at patient
- socioeconomic deprivation assessed using the index of multiple deprivation (IMD) at patient
   level in CPRD and income and educational level in VEGA, latest smoking status (current, past, or
- non-smoker) available only in CPRD, latest alcohol intake (current, past, or no intake) available
   only in CPRD. Demographic variables will be ascertained within the 5 years before ULT initiation,
- 165 gout-related variables: gout duration (years), presence of subcutaneous tophi, number of anti-
- 166 inflammatory prescriptions (colchicine, NSAIDs, and corticosteroids) in 12 months before ULT
- 167 initiation, number of consultations in primary care for gout and number of hospitalisations for

- gout in the 12 months before ULT initiation, ULT molecule (i.e., febuxostat, allopurinol,
   uricosurics) and dose (high vs low starting dose), co-prescription of gout flare prophylaxis with
   colchicine and/or non-steroidal anti-inflammatory drugs on the date of ULT initiation (i.e.,
   prescription length ≥21 days);
- 172 general health and other cardiovascular comorbidities: Charlson Comorbidity Index [28], 173 cardiovascular comorbidities not included in the Charlson Comorbidity index (i.e., hypertension, 174 atrial fibrillation, and hypercholesterolemia), heart failure, diabetes with and without target 175 organ damage, chronic kidney disease (stage 3,4,5), dementia, peripheral vascular disease, 176 COPD, cancer, HIV/AIDS European Society of Cardiology cardiovascular risk (high/very high vs 177 moderate/low), history of cardiovascular events before ULT initiation, number of consultations 178 in primary care for any reason and number of hospitalisations for any cause in the 12 months 179 before ULT initiation,
- 180 medications (low-dose acetylsalicylic acid (ASA), non-ASA antiplatelet agents, statins, fibrates,
- other lipid-lowering agents, potassium-sparing diuretics, thiazides, loop diuretics, beta-blockers,
   calcium-channel blockers, angiotensin-converting enzyme inhibitors and angiotensin receptor

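### The weight model as written does not separate the two arms or state a fitting window, although the arms have opposite censoring rules

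*Protocol*

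**What the plan says.** Under Follow up, the protocol sets two artificial censoring rules. In one arm, "clones assigned to the T2T-ULT arm will be censored at 12 months from ULT initiation if they do not achieve the serum urate target". In the other, clones in "the FAF-ULT arm will be censored at the time they achieve the serum urate target", which can be any month of the first twelve.

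Under Inverse probability of censoring weighing, it gives one description of the weights, a pooled logistic regression described as a "model for the monthly probability of remaining uncensored, including variables for time (in its linear". Time may also enter as a square, and the only other terms that the sentence names are covariates measured at baseline. Truncation at the 99.5th percentile follows, and then a covariate table. The two models in that table are two covariate sets, one common to both databases and one with variables held only in CPRD. They are not one model per arm.

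On timing, the Covariates section says "We will collect the following covariates ascertained on or before ULT initiation to build" the weights. The table nevertheless includes, in both models, "Proportion of days covered by ULT between the date of ULT initiation and the end of" the grace period, which is not known at baseline.

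**The concern.** Each person contributes one clone to each arm, with identical baseline covariates. A characteristic that makes reaching target more likely leads to censoring in the FAF arm and protects against it in the T2T arm. A single coefficient cannot carry both signs, and an arm main effect shifts only the level. The timing differs as well: FAF censoring is spread over twelve months, while T2T censoring is zero for eleven months and then falls on everyone who has not reached target.

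The weights are the plan's only correction for the informative censoring that cloning creates. If they do not vary correctly with the covariates within each arm, the primary comparison is close to attainers against non-attainers without adjustment.

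**Working it through.** The protocol gives no figure for the weights, so there is none to reproduce. The check asks what different readings of the model do when the true effect is nil.

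**Inputs from the protocol** (Feasibility count; Follow up): 28% reach target within a year; MACE rate 17/1,000 person-years; 12-month grace period; 5-year horizon; the two censoring rules; planned difference 1/1,000 person-years.

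**Assumptions, not in the protocol:** one binary baseline factor L with 30% prevalence, a monthly odds ratio (OR) for attainment and a hazard ratio (HR) for MACE.

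**Step 1. The planned difference on the 5-year scale.** [1 - exp(-0.017 × 5)] - [1 - exp(-0.016 × 5)] = 8.15% - 7.69% = 0.46 percentage points.

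**Step 2. What the weights must do (OR 0.5).** A monthly attainment probability of 0.0320 without L has odds 0.0331. Half of that gives a probability of 0.0163 with L. Twelve-month attainment is 1 - (1 - 0.0320)^12 = 32.3% without L and 1 - (1 - 0.0163)^12 = 17.9% with L. Check: 0.7 × 32.3 + 0.3 × 17.9 = 28.0%.

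- T2T weight, 1/Pr(attain): 1/0.323 = 3.10 without L and 1/0.179 = 5.59 with L, so L must be weighted **up**.
- FAF weight, 1/Pr(not attain): 1/0.677 = 1.48 without L and 1/0.821 = 1.22 with L, so L must be weighted **down**.

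A shared model with no arm-by-covariate term moves both arms the same way.

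**Step 3. Size by hand (OR 0.5, HR 2.5).** Prevalence of L after month 12 is 0.3 × 0.179/0.28 = 19.2% in T2T and 0.3 × 0.821/0.72 = 34.2% in FAF. The rate without L is 17/(0.7 + 0.3 × 2.5) = 11.7/1,000, and with L it is 29.3/1,000. Over the remaining four years the risks are 4.6% and 11.1%, a gap of 6.5 points. Unweighted bias is about (0.192 - 0.342) × 6.5 = -0.97 points.

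**Step 4. Full calculation.** Exact expectations, weighted Kaplan-Meier to month 60, true difference 0. Entries are T2T minus FAF in percentage points.

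| Assumed effects | Unweighted | One shared model | Arm-specific, months 1-12 |
|---|---|---|---|
| OR 0.4, HR 2.5 | -1.24 | -1.21 to -1.23 | 0.00 |
| OR 0.5, HR 2.5 | -1.00 | -0.98 | 0.00 |
| OR 0.7, HR 1.5 | -0.23 | -0.23 | 0.00 |
| OR 2, HR 2.5 | +1.20 | +1.23 | 0.00 |

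Adding an arm main effect to the shared model gives -1.02 in the second row and +1.26 in the fourth, so it does not help. A separate random simulation (12 cohorts of 54,000; OR 0.4, rate ratio 2.5) agrees: unweighted -1.13, shared -1.11 to -1.13, arm-specific +0.01.

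**Step 5. The fitting window.** In the T2T arm the monthly censoring probability is 0 to month 11, about 72% at month 12, and 0 afterwards. A logit linear in time over 60 months spreads that spike. Arm-specific fits of this kind leave about -0.35 points (OR 0.4, HR 2.5) or -0.05 (OR 0.7, HR 1.5). With quadratic time over 60 months the remainder is at most 0.02 in size.

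**The case against.** The strongest reply is that the protocol never says the arms share a model. Pooled logistic regression ordinarily means pooling over person-months, and a probability of remaining uncensored makes sense only within an arm, since each person has two clones under opposite rules. Fitting by arm may be intended, and the detail may sit in an analysis plan that is not at hand. This stands: a shared fit is one reading of the text, and on the arm-specific reading, within the grace period, bias from measured baseline factors disappears.

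Three further points also stand. No 60-month window is stated; the Statistical analysis section ties the purpose of the weights to the grace period, and a quadratic term is allowed. It would be wrong to say that the model holds only baseline covariates, because the table adds adherence over the grace period. Size and sign come from assumed effects, and the sign reverses when L raises attainment.

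The reply does not dispose of the matter as a detail for later. The section already fixes the model class, time unit, form of time, truncation point and covariate list. Those terms, followed literally on the stacked clones, give weights that do almost nothing. Negative control outcomes may reveal residual selection, but they do not correct it.

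**Conclusion.** The point holds as a defect in how the primary weight model is specified. As listed, its terms neither separate the arms nor fix a window. On a shared fit the selection from measured baseline factors remains almost whole: 0.23 to 1.23 points in size, or 0.23/0.46 = 0.5 to 1.23/0.46 = 2.7 times the planned difference. On arm-specific fits it is nil over months 1 to 12, and about 0.05 to 0.35 points with linear time over full follow-up. These sizes rest on the assumed prevalence, odds ratios and hazard ratios. That a shared model tracks the unweighted result held in every scenario.

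A reader might infer that the investigators will fit one model to both arms and that the result will be biased in favour of T2T. The document supports neither inference: it is silent on the fit by arm, and the direction depends on which patients attain target.

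Arm-specific fitting also does not deal with common causes of attainment and MACE that are missing from the model, including those arising during the grace period. With one such factor added (prevalence 15%, OR 0.4 to 0.7, HR 1.5 to 2), arm-specific baseline-only fits still left -0.14 to -0.56 points.

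**What to change.** In the section on inverse probability of censoring weights, state that:

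- weights are estimated separately by arm and only within the 12-month grace period;
- in the FAF arm, a monthly pooled logistic model for reaching target is fitted over months 1 to 12 with flexible time;
- in the T2T arm, a single logistic model at month 12 is fitted for having reached target among those still followed;
- artificial-censoring weights are held constant after month 12.

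Also reconcile the baseline-only wording with the table's proportion of days covered. In a monthly model, a value running to the end of the grace period uses future information. Either remove it, or define it as updated only to the month being modelled and say that the model includes a time-varying covariate.

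The cost is a few sentences and a few lines of code, with no new data. If fitting by arm was already intended, only the wording changes.

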### 25 Background and rationale

- 26 Gout is the only form of arthritis that can potentially be "cured" with freedom from recurrent flares
- and disease progression provided long-term treat-to-target urate-lowering therapy (T2T-ULT) is prescribed and adhered with [1]. The goal of T2T-ULT is to achieve and maintain a serum urate
- 29 treatment target of <360 micromol/l [1].
- 30 The T2T strategy is a strategy that defines a treatment and applies tight control (for example, 31 monthly visits and respective treatment adjustments) to reach and maintain this target.
- 32 However, only a suboptimal proportion (around 40%) of patients with gout who start ULT will 33 achieve the serum urate treatment target within 12 months after ULT initiation [2]. Although not
- 34 recommended by international scientific societies, the fire-and-forget (FAF) approach is still widely
- 35 adopted by physicians treating gout patients. It mainly consists of prescribing treatment (e.g., ULT)
- 36 without further dose adjustment based on markers of its effectiveness (e.g., serum urate levels) [3].
- 37 Gout has traditionally been conceptualised as an intermittent inflammatory joint disease. However,
- 38 articular and systemic inflammation during the inter-critical period (i.e. between gout flares) has
- 39 been described recently [4]. Of greater concern, recent publications have demonstrated that flares
- 40 are temporally associated with subsequent cardiovascular events and death due to cardiovascular
- 41 events in the following 30-60 days [5,6]. As T2T-ULT is effective in preventing gout flares after the

42 first year of treatment, long-term T2T-ULT may prevent cardiovascular events and cardiovascular

- 43 mortality by reducing the number of flares [1].
- 44 There is, however, considerable controversy over whether T2T-ULT reduces the risk of adverse 45 cardiovascular events in people with gout, despite the potential for such an effect. Two systematic
- 46 literature reviews showed conflicting results, however, demonstrated several limitations in the
- 47 existing studies' ability to estimate effects on cardiovascular outcomes [7,8]. Firstly, included clinical
- 48 trials that recruited gout patients were underpowered and relatively short (<52 weeks) [7,8].
- 49 Secondly, observational studies that evaluated the association between ULT and cardiovascular
- 50 mortality compared people prescribed ULT with ULT non-initiators so confounding by indication and

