- 183 blockers, other anti-hypertensive agents, nitrates, and oral anticoagulants. Prescriptions will be
- 184 categorised as current (last prescription within 60 days before ULT initiation in CPRD and last
- 185 prescription within 120 days before ULT initiation in VEGA) or past/no prescription. The duration
- 186 was selected based on clinical input as the mean length of prescriptions in the UK and in Sweden
   187 differs.

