### 188 Statistical analysis

- 189 All descriptive statistics will be reported as number (percentage), mean (standard deviation (SD), or
- 190 median (interquartile range (IQR)) as appropriate.
- 191 Although cloning allows us to account for observed confounding at baseline, the artificial censoring 192 introduced is usually informative [12]. The proposed approach to address this problem is to use 193 inverse probability of censoring weighting. The purpose of the weights is to up-weight patients 194 remaining adherent to the protocol so that they represent censored patients, and as such, maintain 195 the comparability of the study arms throughout the grace period. Survival curves will be estimated 196 using a non-parametric Kaplan-Meier estimator weighted for the inverse probability of censoring 197 weights. The 95% confidence intervals for the difference in 5-year survival and the difference in 198 restricted mean survival times will be obtained using a non-parametric bootstrap with 1000 199 replicates [29].
- 200 First, data from Sweden and the UK will be analysed separately. Then, results will be meta-analysed.
- 201 All analyses will be performed using Stata, version 18 (StataCorp, Texas, USA).

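### Apart from one forward-looking ULT coverage variable, the censoring weights use only covariates fixed at or before ULT initiation, so comparability over the 12-month grace period may not be achieved

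*Protocol*

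**What the plan says.** The section *Inverse probability of censoring weighing* specifies a pooled logistic model fitted by month, whose predictors are time terms plus data from initiation or earlier: "and/or quadratic terms depending on the data structure) and the baseline covariates". The *Covariates* section fixes the timing: "We will collect the following covariates ascertained on or before ULT initiation". Gout contacts are counted over the preceding year ("gout in the 12 months before ULT initiation"), as are anti-inflammatory prescriptions and all-cause contacts. Other drugs are classed by a look-back from initiation, 60 days in CPRD and 120 days in VEGA ("categorised as current (last prescription within 60 days before ULT initiation in CPRD and last").

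One row of the weight table, marked for both models, is measured after baseline ("Proportion of days covered by ULT between the date of ULT initiation and the end of"); its window runs to the close of the grace period. It does not appear in the *Covariates* list.

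Under *Follow up*, FAF clones are censored whenever target is reached within 12 months, and T2T clones at month 12 if it has not been reached. *Statistical analysis* calls such censoring usually informative and gives the weights this task: to preserve "the comparability of the study arms throughout the grace period". *Background and rationale* reports a link between flares and cardiovascular outcomes over the next 30 to 60 days ("are temporally associated with subsequent cardiovascular events and death due to cardiovascular").

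**The concern.** Cloning already makes the arms identical at time zero. The weights are there to deal with what happens afterwards, when clones leave an arm because target was or was not reached. If a patient is admitted, develops CKD, heart failure or diabetes, starts a diuretic or keeps flaring during that year, the event may change both the chance of a recorded urate at target and the risk of MACE. A model that knows only the patient's state at initiation gives the same weight to patients who became ill and to those who did not. The clones left in each arm then differ in risk even if the strategy has no effect. What is at stake is a spurious 5-year difference, possibly similar in size to the one the study wants to detect.

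**Working it through.** **1. The plan's own yardstick.** *Feasibility count and sample size considerations* gives 17 per 1,000 person-years in the unexposed and a difference of 1 per 1,000. With constant rates and the exposed at 16 per 1,000:

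- 1 − exp(−5 × 0.017) = 8.15%
- 1 − exp(−5 × 0.016) = 7.69%
- Difference sought: 0.46 percentage points (pp) at 5 years.

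**2. What the weights contain.**

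| Grace-year information | In either weight model? |
|---|---|
| Flares, anti-inflammatory prescriptions | No; year before initiation only |
| Gout and all-cause contacts, admissions | No; year before initiation only |
| New comorbidity | No; on or before initiation |
| New cardiovascular or diuretic drugs | No; 60 or 120 days before initiation |
| Serum urate during follow-up | Not listed |
| ULT coverage | Yes, but as one whole-period summary |

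In a model for month 3, the coverage row uses supply from months 4 to 12, which is not yet known. It is also not a baseline covariate, so text and table disagree.

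**3. Deterministic check under a true null.** Inputs from the protocol: 17 per 1,000 person-years and 28% at target by 12 months. Assumed inputs: a marker acquired with probability p per month in year 1, which multiplies the MACE hazard by HR and the monthly chance of reaching target by r. There are no baseline covariates, so baseline-only weights are constant within an arm and month and cancel. Risk in each arm is 1 − Π(1 − h_t), where h_t is the mean hazard among clones still in that arm. Bias is the T2T minus FAF risk at 5 years.

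| Marker | p | HR | r | Bias |
|---|---|---|---|---|
| Permanent | 1% | 2 | 0.5 | −0.22 pp |
| Permanent | 1% | 2 | 1.5 | +0.19 pp |
| Permanent | 1% | 2 | 2 | +0.36 pp |
| Lasts 2 months | 0.5–5% | 2–3 | 0.5–2 | at most about 0.012 pp, either sign |

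Over p = 0.5–2%, HR 2–3 and r = 0.5–0.7, the permanent marker gives about 0.07 to 0.7 pp in favour of T2T. The FAF arm alone contributes about 0.03 to 0.20 pp when r = 0.5. The rest comes from the T2T arm.

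**4. Simulation with fitted weights, true null.** Six runs of 150,000 people, one baseline covariate, and a lasting marker acquired by 26% in year 1. Between 30% and 34% reached target, and weights were not truncated. The T2T minus FAF 5-year risk difference, in pp:

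| HR for MACE | OR for target | Baseline-only weights | Marker updated monthly |
|---|---|---|---|
| 1 | 1 | −0.08 (SE 0.13) | −0.08 (SE 0.13) |
| 1.5 | 0.7 | −0.31 (SE 0.16) | −0.12 (SE 0.17) |
| 2 | 0.5 | −0.67 (SE 0.18) | +0.07 (SE 0.21) |
| 3 | 0.5 | −1.32 (SE 0.22) | +0.06 (SE 0.28) |
| 2 | 1.5 | +0.52 (SE 0.11) | +0.01 (SE 0.11) |

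The weak case is not clearly separated from noise. In the stronger cases, time-updated weights remove the bias to within simulation error. The sign follows the marker's effect on attainment.

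**5. Cost of month-by-month weights in the T2T arm.** Take 46,000 clones, 28% attainment and a constant monthly hazard, and ignore first-year events:

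- Monthly chance of attainment: 1 − 0.72^(1/12) = 0.0270
- Attain in months 1–11: 46,000 × (1 − 0.973^11) ≈ 11,960, weight 1
- Attain in month 12: 12,880 − 11,960 ≈ 920 (2% of clones), weight 1/0.0270 ≈ 37
- Effective sample size: 46,000² / (11,960 + 920 × 37²) ≈ 1,660.

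So 2% of clones would stand for the 74% not at target by month 11. Because those 920 are about 7% of the 12,880 attainers, truncating their weights at the 99.5th percentile would not trim them.

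**The case against.** The strongest counter-arguments are these.

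- **The weights are not purely baseline.** This is correct. ULT coverage is a main route by which illness could prevent attainment, and it is in both models. It does not cure the problem: it records none of the other events, is not updated by month and looks ahead.
- **The direction is not settled.** A reader might infer that sick patients fail to reach target, stay in FAF and so flatter T2T. The documents do not support this. An admission or flare can also prompt a consultation and a urate test, and a recorded urate is required to count as at target. The sign then reverses, as shown above.
- **Flares alone may not matter.** A reader might take the cited flare association as proof of material bias. It describes risk over 30 to 60 days, and a two-month risk of that kind produces almost nothing at 5 years. Persistent flare activity could matter more, but prior-year gout contacts and anti-inflammatory prescriptions, already in the weights, capture part of it.
- **There are safeguards.** Negative control outcomes may flag residual confounding, and the analysis excluding FAF patients without a urate test bears on the testing route. Both help interpretation, but neither changes the weights.
- **A separate SAP may exist.** That does not answer the point, because the protocol itself fixes the covariate set in text and table.

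**Conclusion.** The point holds as a risk of bias built into a stated rule. Apart from whole-period ULT coverage, no grace-year information enters the weights, so they may not deliver the comparability the plan asks of them. It would go too far to say that they certainly fail: bias arises only if a grace-year factor predicts both censoring and MACE. The documents give a link from flares to cardiovascular events, but no onset rates, no hazard ratios for new illness and no effect of any such factor on attainment.

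On assumed inputs the size ranges from about 0.01 pp for short-lived risk to several tenths of a point for lasting new illness. It exceeds 1 pp only in the most extreme scenario (a quarter of patients affected, HR 3, odds of attainment halved). The benchmark is 0.46 pp, and either sign is possible. The plan should be changed, since the model is already monthly and the records are already linked.

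**What to change.** - Add month-updated covariates, lagged one month, to the pooled logistic model: flares or anti-inflammatory prescriptions, gout and all-cause contacts, admissions, new comorbidity (CKD stage, diabetes, heart failure), new cardiovascular or diuretic drugs, and last serum urate.
- Replace whole-period ULT coverage with coverage accrued to the previous month.
- Reconcile the *Covariates* section and the text of *Inverse probability of censoring weighing* with the table.
- Show weighted balance of these factors at month 12, and keep the baseline-only version as a sensitivity analysis.
- In the T2T arm, where artificial censoring occurs only at month 12, use covariates updated to that point and say how values recorded after attainment are handled. Examine the weight distribution and effective sample size before adopting month-by-month attainment weights.

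No new data are needed: primary care and hospital records are already linked, and flares are already a secondary outcome. The cost is more data preparation and more variable weights. In the T2T arm the loss of precision could be substantial, and that is a real trade-off. The FAF-arm change does not depend on how it is resolved.
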